COMIRB Protocol

COLORADO MULTIPLE INSTITUTIONAL REVIEW BOARD
[name] [contact] [contact]

Protocol #: 17-1697

Project Title: A Multicenter Trial of a Shared DECision Support Intervention for Patients offered implantable Cardioverter-DEFibrillators: DECIDE - ICD Trial

Principal Investigator: [name], MPH

Version Date:

I. Hypotheses and Specific Aims:

The research team proposes to assess the real-world effectiveness and implementation of patient decision aids (PtDA) for high-risk decisions using the implantable cardioverter-defibrillator (ICD) as a model.

Hypotheses

- 1a) *Decision aids will reach over 50% of eligible patients.*
- 1b) *ICD PtDAs will be effective in improving decision quality in real-world practice.*
- 1c) *Better informed patients will have lower anxiety, higher rates of planning for the possibility of deactivation, and increased identification of a surrogate decision maker.*

Specific Aims

- 1) *Assess real-world effectiveness of PtDA for high-risk decisions using the ICD as a model.*

II. Background and Significance:

Patient-centered care is growing in both practical and political importance. As the primary process of involving patients directly in their care, SDM is explicitly supported both by the IOM^{1,2} and in the Affordable Care Act.³ The Food and Drug Administration has recently begun the Patient Preference Initiative and is considering SDM as part of the approval process.⁴ Medicare recently included requirements for SDM as a condition of reimbursement for lung cancer screening⁵ and the left atrial appendage closure (WATCHMAN) device placement.⁶ Our group takes a broad view of SDM as a “meeting between experts.”⁷ This definition from 1985 acknowledges the clinical expertise of the clinicians and the lived expertise of the patients. We reject incorrect assumptions that SDM is just presenting information to patients and asking them to choose.⁸ Rather, SDM is an intimate process between patients and clinicians whereby treatment recommendations are tailored to both the best evidence and well-informed patient preferences.

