*Despite their established efficacy, PtDAs are not implemented outside the research setting.*³⁶ Much of the prior work on PtDA implementation has occurred in primary care settings with lower-risk interventions.^{30,36,37} A recent systematic review of PtDA implementation (co-author [name] – Co-I) identified a host of logistical barriers, including clinicians' perception of time necessary to use PtDAs, lack of reimbursement, and perceived bias inherent in the PtDAs themselves. As described above, ICDs are a higher risk treatment with significant trade-offs. Professional guidelines and proposed quality measures recommend SDM.^{38,39} However, we have shown that clinician opinions vary⁴⁰ and many clinicians endorse paternalistic views which de-emphasize patient preferences out of fear that patients may "make an unwise decision and not proceed with therapy."²⁹

This proposal builds on prior lessons learned. We have identified many problems in the field of SDM and PtDAs. With this innovative type II effectiveness/implementation hybrid design,⁴¹ we will study solutions to these problems (**Table 1**). We assert that the combination of the high-risk nature of the decision, the engaged study team of clinical champions, a user-centered approach to PtDA development, a reproducible implementation strategy, and recent changes in professional guidelines will lead to implementation success.

Table 1: Problems and Solutions Addressed

Conceptual Area		Problem	Our Solution
Aim 1	1a: Reach	Unclear how to best reach eligible	A suite of 3 decisions aids and clinical

		patients	champions will assist in normalizing the new process.
	1b. Effectiveness	Lack of data regarding educational outcomes in real-world practice	Exploring effectiveness in a real-world trial rather than a tightly controlled research setting.
	1c: Downstream effects	Lack of data regarding QOL impact of SDM in real-world practice	Test the hypotheses that better informed patients have improved psychosocial outcomes.

III. Preliminary Studies/Progress Report:

Section 1: Strength of our infrastructure and investigators

Our transdisciplinary research team has an established record of success in a broad range of topics related to SDM development, measurement, ICDs, and implementation (**Table 2**).

	Core team	Expertise in SDM	Expertise in implementation	Expertise in ICDs	Analytic team
[name], MPH, Project Lead	X	X	X		X
[name], MHS, Co-I	X	X	X	X	
[name], MPH, Co-I	X	X	X		
[name], MSW, Co-I	X	X			X

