- Modular design: The sectional build of the PtDAs—clearly defined pages for the pamphlet and segmented video—allows for simple revision as problems are identified or information changes over time.

F. Data Analysis Plan:

Quantitative analysis (Hypotheses 1a, 1b, 1c): The analyses of the effectiveness will use a repeated measures mixed model. This strategy allows for partially incomplete data (e.g. missing follow-up or one of the collection periods) and relaxes the missing data assumptions to missing at

random conditional on observed data. Prior to these analyses, we will contrast the participants in the 2 phases of the study, identifying any patient/site characteristics that are unbalanced. If more than 3-5 variables are identified, we will develop a propensity score for the likelihood of being in the intervention phase. Each analysis model will include an indicator variable for the intervention phase, indicators for each of the sites and the variables identified above.

Sample Size and Power Calculation: This trial was designed to have diversity in implementation settings. As such, to effectively be powered to explore implementation across diverse settings, we are overpowered to test our primary quantitative outcomes (the knowledge domain of decision quality). With a sample size of 900 patients and a standard deviation of 18%, achieved power would approach 1.00 to detect a 10% improvement in knowledge (in the 2011 Cochrane Review, knowledge improved an average of 13.8%, in our pilot trial, knowledge improved 12%).⁶ Even with variance inflation for correlation within sites (assuming intraclass correlation 0.01), the power remains good at 0.98. This level of power will afford the ability to assess some heterogeneity of effect across sites and vulnerable patient groups, as well as adequate assessment of secondary effectiveness measures and implementation evaluation. To test the hypothesis that better informed patients will have less anxiety (hypothesis 1c), we will correlate the knowledge score with the HADS- A. Using a Pearson's correlation coefficient, for a sample size of 300 (based on 1/3 illustrating significant anxiety) then the person's correlation is 0.18 for a power of 90% and an alpha of 0.05.

G. Summarize Knowledge to be Gained:

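### For two of the three hypothesis 1c outcomes, the only stated analysis compares trial phases and has no knowledge term, so it does not test whether better informed patients plan more

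*Combined protocol and SAP*

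**What the plan says.** Section I states hypothesis 1c as "Better informed patients will have lower anxiety, higher rates of planning for the possibility of deactivation, and increased identification of a surrogate decision maker". Table 1 in section II gives the same aim: "Test the hypotheses that better informed patients have improved psychosocial outcomes". In both places the exposure is being informed, not the trial phase.

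Section IV.F opens its analysis paragraph with "Quantitative analysis (Hypotheses 1a, 1b, 1c): The analyses of the effectiveness will use a repeated measures mixed model". It then lists the terms: "Each analysis model will include an indicator variable for the intervention phase, indicators for each of the sites and the variables identified above". The variables referred to come from a comparison of the two phases, "identifying any patient/site characteristics that are unbalanced". Section IV.C (Overview) says that patient-centred outcomes are compared before and after implementation in order to judge the intervention.

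Knowledge enters a test of 1c once, in the sample-size paragraph of IV.F, and only for anxiety: "To test the hypothesis that better informed patients will have less anxiety (hypothesis 1c), we will correlate the knowledge score with the HADS- A". No knowledge-based test and no power figure is given for deactivation planning or surrogate identification. The related survey items are part of ICD experiences (section IV.A). Table 5 schedules these at 1 and 6 months, the same visits as the post-decision knowledge score.

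**The concern.** The null of 1c for these outcomes is that planning does not depend on what the patient knows. The null of the stated model is that planning does not differ between control and intervention phases. Either can be true while the other is false.

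- Knowledge varies widely within each phase (SD 18 points in IV.F) and the phase is expected to move it by about 10. A real knowledge association therefore reaches the phase contrast much diluted.
- The aids include guidance on deliberating and communicating (section III). They could lead a patient to raise deactivation or a surrogate whatever the patient's knowledge score. Phase would then differ with no knowledge association.

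At stake is whether the trial can answer two thirds of a numbered hypothesis. A significant phase coefficient would not show that better informed patients plan more, and a null one would not show that they do not.

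**Working it through.** **Inputs from the documents.** N = 900, knowledge SD 18, gain 10 points (also cited: 12 in the pilot, 13.8 in a review), ICC 0.01, and for anxiety r = 0.18 with n = 300 (all IV.F); 6 randomised sites (IV.C); Cronbach's alpha of the knowledge score 0.61 (section III).

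**Assumptions.** Two-sided 5% tests, since sidedness is not stated. r = 0.18 is borrowed from the anxiety calculation. Base rates of planning are 15%, 30% and 50%, and the split between phases is assumed. The documents give none of these for the two outcomes. No calendar-time term is used, because the stated model lists none.

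**The plan's own figures.** For anxiety the plan says "correlation is 0.18 for a power of 90% and an alpha of 0.05". Fisher z: Φ(atanh(0.18) × √297 − 1.96) = Φ(3.136 − 1.96) = 0.88, within 2 points of 0.90. For knowledge, 450 v 450: 10 / (18 × √(2/450)) = 8.33, so power is about 1.00. With design effect 1 + 149 × 0.01 = 2.49, power is above 0.99, against 0.98 stated. The plan's inputs are usable.

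**Power of the phase contrast if knowledge is the only pathway.** The outcome shifts by r × (gain/18) SD units, and power = Φ(r × (gain/18) × √(900w) − 1.96). Here w is the average within-site variance of the phase indicator:

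- half of each site's patients in each phase: w = 0.25, √(900w) = 15
- staggered switching, site k having k/7 of its patients in one phase: w = (56/49)/6 = 0.190, √(900w) = 13.09

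| Setting | Shift (SD) | Half/half | Staggered |
|---|---|---|---|
| r = 0.18, 10 points | 0.100 | 0.32 | 0.26 |
| r = 0.18, 12 points | 0.120 | 0.44 | 0.35 |
| r = 0.18, 13.8 points | 0.138 | 0.54 | 0.44 |
| r = 0.30, 10 points | 0.167 | 0.71 | 0.59 |
| r = 0.18, 10 points, reliability 0.61 | 0.100/0.61 = 0.164 | 0.69 | 0.57 |

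The last row supposes that SD 18 includes measurement error and that the aid shifts true knowledge. In the first row the phase difference is 0.100 × √(p(1 − p)), which is 3.6, 4.6 and 5.0 percentage points at base rates of 15%, 30% and 50%. With a 10-point gain, power reaches 50% at r = 0.235 (half/half) or 0.27 (staggered).

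Simulated logistic models (6 sites of 150, 1,500 runs per setting) gave 0.24 to 0.36 for the first row across the three base rates. Incomplete follow-up lowers power: at an assumed 80%, the staggered 0.26 becomes 0.22.

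**Power of a knowledge term.** Φ(atanh(r) × √897 − 1.96) gives 0.85 at r = 0.10 and above 0.99 at r = 0.18, with no confounding. If adjustment left a spurious correlation of 0.05 (assumed), the same formula gives Φ(1.499 − 1.96) = 0.32 as the rate of wrong rejection.

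**The opposite case.** Knowledge was given no association with the outcome, and the aid a direct effect. With an assumed odds ratio of 1.8 at a 30% base rate, staggered, the phase test was positive in 95% of runs and the phase-adjusted knowledge test in 3%. With an assumed direct effect of 10 percentage points, the phase-and-site test was positive in 76% to 90% of runs.

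**The case against.** The strongest reply is that IV.F never assigns these two outcomes to the phase coefficient. It says what each model will include, which does not exclude a knowledge term; a model with knowledge, phase, site and covariates would satisfy the sentence. Anxiety falls under the same paragraph heading and still has its own knowledge correlation. This stands: the term is absent by omission, and a reader who inferred that the plan prescribes the wrong test or rules out the right one would go too far. It does not remove the gap, because no knowledge-based test is prespecified and the only comparison described is before against after.

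Second, the phase contrast has a proper purpose. It draws on the randomised rollout and addresses the effect of the aids. That also stands, and it should be kept for that purpose.

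Third, the numbers could be read to mean that the trial would usually miss 1c when it is true. The documents do not support that as a general statement. The r of 0.18 belongs to anxiety, no association or base rate is given for planning, and power passes one half under several settings above.

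Fourth, the near-certain power of a knowledge term could be read as making it the safer test. That figure assumes no confounding. Section III reports that knowledge differs by age and education, and a small residual correlation would inflate false positives, as shown.

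**Conclusion.** The point holds as a mismatch between hypothesis and analysis. For deactivation planning and surrogate identification, the stated analysis is a phase contrast, and no result from it can settle whether better informed patients plan more. This rests on the text alone.

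The size is conditional. If knowledge is the only pathway, phase-contrast power for a knowledge association is about 25% to 35% at r = 0.18 and a 10-point gain. It is about 45% to 70% with a 13.8-point gain, r = 0.30, or reliability of 0.61. A stronger association would do better still, so low power should be quoted with its assumptions. The opposite error, a positive phase result with no knowledge association, needs a direct effect of the aid, whose size here is assumed.

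This is a cheap improvement. It affects two secondary outcomes of a numbered hypothesis and leaves the primary outcome and the anxiety test untouched.

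**What to change.** In section IV.F, state that for deactivation planning and for surrogate identification, each scored yes/no, hypothesis 1c is tested by the coefficient of the post-decision knowledge score. Use a logistic model, or its repeated-measures equivalent, adjusted for phase, site and collected covariates: age, education, literacy and numeracy. Add decision type (initial implant, reimplantation or CRT) if it is recorded; neither Table 5 nor the data-collection paragraph lists it. Fix in advance which knowledge visit is paired with which response visit.

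Report the coefficient as an adjusted association open to residual confounding. Report the phase contrast for the same outcomes separately, as the effect of the decision aids.

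The cost is a few sentences and two models. Knowledge and ICD experiences are already scheduled together at 1 and 6 months, so no patients or visits are added. The downside is that knowledge is not randomised, and that patients without a knowledge score must be imputed or drop out of the model; the plan should say which.

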Implantable cardioverter-defibrillators (ICD) are an ideal model to implement SDM. Over 200,000 ICDs are implanted annually (both new devices and replacements)⁹ in an effort to prevent sudden cardiac death (SCD), a leading cause of death in the US. Once surgically implanted, the ICD monitors the patient’s heart for dangerous rhythms, quickly delivering a defibrillation shock to restore a healthy rhythm. Despite their clinical utility in improving mortality from SCD,^{10-12,13} a number of clinical and quality of life (QOL) threats exist. Some studies suggest that patients with ICDs have more heart failure admissions,¹⁴ a lower quality of life— particularly if shocked^{15,16}—and an increased incidence of anxiety, depression, and post-traumatic stress disorder.¹⁷ Further, ICDs can fail,¹⁸ shock inappropriately,¹⁹ and, if not properly deactivated cause unnecessary suffering at the end of life.²⁰⁻²³ Patients have described an ICD shock as “getting kicked in the chest by a mule”²⁴ leading some to have their ICDs removed for fear of repeated shocks.²⁵

Patients with ICDs may face multiple preference-sensitive decisions. Patients recommended for primary prevention ICD therapy face the ICD decision in several contexts: 1) initial implantation (130,000/year); 2) re-implantation when an existing battery dies after 5-7 years (70,000/year); and 3) when considering whether to include defibrillation in cardiac resynchronization therapy (CRT) (40% of ICDs).⁹ Each decision hinges on whether the patient's goals align with accepting a device in the hope of extending life, while foregoing the possibility of sudden death. Patients facing this decision may intuitively seize the opportunity to prevent sudden death, but many of the same patients also intuitively indicate that they would prefer to die peacefully in their sleep, which the ICD prevents.²⁶

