- Patients declining ICDs expressed concerns that the numbers didn't apply to them and/or the benefits were not enough: "It's like walking around with a motorcycle helmet on when you're driving your car." One patient addressed the trade-off between dying sooner from sudden death and living longer and dying of progressive heart failure: "Going into my decision is also the fact that I can't work because of my medical condition. I can't work at the hospital; I can't work at the church. My life is sitting here and watching TV... to take a defibrillator would just lengthen the process that I don't really want lengthened."
- Behavioral economics were applied via a framework analysis of two sets of interviews. We found evidence of cognitive bias in decision making, including patients attributing a halo effect to a clinician, who then presents a status quo bias to perform an ICD in the context of influential framing techniques. Taken together, the biases appeared to encourage ICD treatment.(under review)

Development of a measure of decision quality: Decision quality is an essential element of the Ottawa Decision Support Framework (Figure 2) defined as "the extent to which the implemented decision reflects the considered preferences of a well-informed patient."⁵⁵ Accordingly, a decision is "a quality decision" if the treatment chosen is concordant with a knowledgeable patient's values.^{55,56} Some have proposed that measures of decision quality be included in the pay for performance agenda⁵⁷ and the Affordable Care Act calls for "the development of quality measures that allow for the assessment of the experience, quality, and use of information provided to and used by patients..."³ We developed a measure of ICD decision quality using a robust process of patient and clinician assessment to determine the key knowledge items (content validity). We then tested this measure on a large population of patients and determined test-retest reliability ($r=0.56$, $p>.01$) and internally-reliable assessment of patient knowledge ($\alpha=.61$). We demonstrated discriminant known-groups validity of the knowledge measure by showing that clinicians scored better than patients with ICDs who scored better than patients without ICDs (98% vs. 60% vs. 40% mean scores, respectively).

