Stepped-wedge multicenter trial (Table 3): We considered three potential designs for this trial. A classic patient-level randomization is not possible since programs (rather than patients) are effectively the primary targets of intervention implementation. The traditional cluster randomized trial would be disadvantaged by the small number of sites. Therefore, we propose a multicenter trial that is randomized at the clinic-level for a phased rollout of the shared decision support intervention.^{42,84} A variant of the cluster trial design, the stepped-wedge trial design is a one-way crossover cluster trial where all the groups will receive the intervention, but the time of intervention is randomly ordered. It is a compelling choice of design when 1) one of the goals is to study intervention implementation, 2) the intervention is thought to be efficacious, 3) all sites wish to receive the intervention and continue its implementation after the trial if it is effective, and 4) contamination/diffusion of the intervention effects to other subjects is likely. The stepped-wedge design is more efficient in terms of statistical power when compared to the classical cluster randomized design because the impact of the intervention is estimated using both within and between cluster differences.

Table 5: Measures	Baseline Pre Decision	1 Month Post Decision	6 Months Post Decision
-------------------	-----------------------	-----------------------	------------------------

COVARIATES			
- Demographics (combined survey and short chart review)	X		
- Medications, Comorbidities, Heart Failure Type/Severity	X		X
- Literacy (REALM-R 7 item) ⁸⁵ and Subjective Numeracy ⁸⁴	X		
EFFECTIVENESS OUTCOMES (see descriptions below)			
- Decision Quality – Knowledge	X	X	X
- Decision Quality – Value-concordance	X	X	X
- Decision Process		X	X
- Decision choice		X	X
- Self-Efficacy Scale	X	X	X
- Control Preferences	X	X	X
- Decision conflict	X	X	X
- Decision regret		X	X
- PHQ-2	X		X
- GAD-2	X		X
- ICD Experiences (+/- shock; +/- complications etc.)		X	X

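### The anxiety test for hypothesis 1c is an unadjusted correlation in a sample that mixes patients with and without an existing ICD, so device status can mask a benefit or suggest a spurious harm

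*Combined protocol and SAP*

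**What the plan says.** Section I states 1c directionally: better informed patients are expected to have lower anxiety. The only place that spells out a test of this part is the sample size paragraph of Section IV.F: "To test the hypothesis that better informed patients will have less anxiety (hypothesis 1c), we will correlate the knowledge score". The anxiety scale named there is HADS-A. The statistic and the number of patients follow: "Using a Pearson's correlation coefficient, for a sample size of 300 (based on 1/3 illustrating significant anxiety"). For that number the plan gives a detectable correlation of 0.18, at 90% power and a 5% significance level. It names no covariate, stratum or time point.

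The Data Analysis Plan paragraph just before it also lists 1c, under a repeated measures mixed model. The terms of that model are study phase, site, and any characteristics found to be unbalanced between the two phases.

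Four other places bear on the point:

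- Section IV.B enrols initial implants, reimplantations and CRT with defibrillation together.
- Section III, on developing the decision quality measure, reports that "clinicians scored better than patients with ICDs who scored better than patients without ICDs", with mean scores of 98%, 60% and 40%.
- Section II says some studies suggest that patients with ICDs have, among other problems, "an increased incidence of anxiety, depression, and post-traumatic stress disorder". It gives no size.
- Table 5 schedules knowledge at baseline, 1 month and 6 months, and anxiety (GAD-2) at baseline and 6 months. It also lists "ICD Experiences (+/- shock; +/- complications etc".) after the decision. HADS-A is not in the table.

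**The concern.** A variable that is positively related to both members of a pair adds a positive term to their raw correlation. By the protocol's own statements, having an ICD goes with higher knowledge and, in some studies, with more anxiety. The enrolled sample varies in device status by design. The hypothesis predicts a negative correlation, so this term works against it. A real benefit of being informed could be missed, or, with no true relation, patients who know more could appear to be harmed. Nothing in the plan removes this term. Device status would enter the mixed model only if it happened to be unbalanced between phases, and that model does not estimate the relation between knowledge and anxiety in any case.

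**Working it through.** **The plan's own figure.** Fisher z, two-sided alpha 0.05, N = 300, r = 0.18: atanh(0.18) × √297 − 1.960 = 0.1820 × 17.234 − 1.960 = 1.176, so power is 0.880. Exactly 90% needs N = 321, or r = 0.186 at N = 300. The stated figure is reproduced to within two points.

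**Inputs from the protocol.**
- Knowledge gap by device status: 60 − 40 = 20 points (Section III).
- Knowledge SD: 18 points (Section IV.F), taken as the within-group SD. The gap is then 20/18 = 1.11 SD.

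**Assumed inputs.**
- Share with a device, p: the trial's mix is not given. The national volumes in Section II (130,000 initial, 70,000 reimplantations) give 70/200 = 35%. Because only p(1−p) enters, 65% gives the same results. 90% is used to represent a 6-month survey at which most patients have a device.
- Anxiety gap by device status, d_a: not given. Range 0.1 to 0.5 SD.

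**Formulas.** With q = p(1−p) and d_k = 1.11:
- r_k = d_k√q / √(1 + d_k²q), and r_a has the same form with d_a.
- Induced r when knowledge has no relation to anxiety within device groups: r_k × r_a.
- Raw r when the device-adjusted r is −0.18: −0.18 × √[(1−r_k²)(1−r_a²)] + r_k r_a.

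**Results for p = 0.35 (or 0.65).** q = 0.2275 and r_k = 0.468.

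| d_a (SD) | r_a | Induced r | Raw r if adjusted r is −0.18 | Power, N = 300 | Chance of significant positive r if no true relation: N = 300 / N = 900 |
|---|---|---|---|---|---|
| 0.1 | 0.048 | +0.022 | −0.137 | 66% | 6% / 10% |
| 0.2 | 0.095 | +0.044 | −0.114 | 50% | 12% / 27% |
| 0.3 | 0.142 | +0.066 | −0.091 | 35% | 21% / 51% |
| 0.5 | 0.232 | +0.109 | −0.046 | 12% | 47% / 90% |

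Without confounding, power is 88% and the chance of a significant positive result is 2.5%.

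**Results for p = 0.90.** The induced r runs from +0.009 to +0.047. A device-adjusted −0.18 appears as −0.161 to −0.122, with power of 80% to 56%. The chance of a significant positive result at N = 300 is 4% to 12%.

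**Sign reversal.** The raw r reaches zero when d_k × d_a × q = 0.18, that is, d_a = 0.18 / (1.11 × 0.2275), or just over 0.71. A gap of about 0.72 SD or more is needed at p = 0.35.

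**Cost of adjusting.** With k covariates, √(N−3) becomes √(N−3−k). For a partial r of 0.18 at N = 300, power is 0.879 with one covariate and 0.873 with seven. With twelve it is 0.867 (0.1820 × √285 − 1.960 = 1.112).

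**The case against.** The best defence is that Section IV.F places 1c under the mixed model, that Section IV.A lists GAD-2 as a secondary effectiveness outcome, and that the Overview in Section IV.C says such outcomes will be compared before and after implementation. A reader might infer from the correlation sentence that no phase comparison of anxiety is planned. The documents do not support that: the comparison is largely planned. What stands is that it answers a different question, the effect of the decision aid rather than of being better informed. The sentence that says how 1c will be tested still specifies the raw correlation, so the two paragraphs have to be reconciled.

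Second, a reader might infer that the protocol says an ICD raises both knowledge and anxiety. It does not. The anxiety statement is hedged and has no size. The 60% against 40% is a cross-sectional known-groups contrast, and the patients without ICDs are not described. Trial patients without a device have all been offered one, so the gap may be smaller among them. Association is as far as the text goes.

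Third, device status is not the only candidate confounder. A survey described in Section III links older age and less education to lower knowledge. The protocol does not say how these relate to anxiety in this population, so the net direction of all confounding is not established. This argues for adjustment, not for leaving the correlation raw.

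Fourth, the sizes rest on assumed gaps, and the bias is small at the low end or when nearly everyone has a device. That is correct, and the range above shows it.

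**Conclusion.** The concern holds as a foreseeable confounder that the plan leaves uncontrolled. With 35% or 65% of patients having a device and an anxiety gap of 0.1 to 0.5 SD, device status alone induces a correlation of about +0.02 to +0.11, or 12% to 60% of the planned 0.18 and in the opposite direction. Power for a true −0.18 would fall from 88% to between 66% and 12%. The loss is milder, to between 80% and 56%, if 90% have a device. The device share and the anxiety gap are both assumptions. The figures also take the 20-point knowledge gap to carry over to trial patients and anxiety to be analysed over its full range. If the 300 are only the patients with significant anxiety, the figures would change.

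A reader might infer that a real benefit of the targeted size would change sign. Across the assumed range it would not: that needs a gap of about 0.72 SD. The realistic risks are a masked benefit or, with no true relation, an apparent harm. 1c is not the primary hypothesis, and the knowledge comparison on which the trial is powered is unaffected.

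**What to change.** Replace the raw Pearson test with a regression of 6-month anxiety on 1-month knowledge, so that knowledge is measured before the outcome. Adjust for baseline anxiety, existing ICD at enrolment, site, phase, age and education. Implant type gives existing ICD directly for initial implants and reimplantations. Where the CRT category leaves it open, take it from the medical history.

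Name GAD-2, the scale collected at baseline and 6 months, in place of HADS-A. State which patients are analysed, since the basis for 300 is unclear.

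Report the planned phase comparison of 6-month anxiety, adjusted for baseline anxiety, alongside this regression. Say in Section IV.F that the phase comparison addresses the decision aid and the regression addresses being better informed.

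Use ICD in place at the survey and shocks only in sensitivity analyses. Both can follow from the informed decision, so adjusting for them in the main model could remove part of the effect of interest.

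The cost is a change of wording. The variables are in Table 5, the Section IV.C data collection list or the eligibility information, and power at N = 300 goes from 0.880 to about 0.87. The result remains an observational association, since other confounders may persist, and should be reported as such.
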